### 10.1.3. CONFIDENTIALITY AND PRIVACY

Participant confidentiality and privacy is strictly held in trust by the participating investigators, their staff, and the sponsor(s) and their interventions. This confidentiality is extended to cover testing of biological samples in addition to the clinical information relating to participants. Therefore, the study protocol, documentation, data, and all other information generated will be held in strict confidence. No information concerning the study or the data will be released to any unauthorised third party.

All research activities will be conducted in as private a setting as possible.

Human Ethics Committee, Therapeutic substances committee or pharmaceutical company supplying study product may inspect all documents and records required to be maintained by the investigator, including but not limited to, medical records and pharmacy records for the participants in this study. The clinical study site will permit access to such records.

The study participant's contact information will be securely stored at the clinical site for internal use during the study. At the end of the study, all records will continue to be kept in a secure location for 15 years.

Study participant research data, which is for purposes of statistical analysis and scientific reporting, will stored at the on the intranet at the Women's and Children's Hospital. This will not include the participant's contact or identifying information. Rather, individual participants and their research data will be identified by a unique study identification number. The study data entry and study management systems used by research staff will be secured and password protected. At the end of the study, all study databases will be de-identified and archived at the Women's and Children's Hospital.

---

### 10.1.4. FUTURE USE OF STORED SPECIMENS AND DATA

Not applicable

---

### 10.1.6.SAFETY OVERSIGHT

Safety oversight will be under the direction of the **Human Research Ethic Committee (HREC)** at the Women's and Children's Hospital. **[name], consultant paediatric anaesthetist will act as a medical monitor for this trial. All adverse effects and complications will be reported to him for review and presentation to the HREC. [name] is independent from the study conduct and free of conflict of interest.** The investigators will immediately report any serious adverse events (SAE) to the **HREC** and all adverse events (AE) will be presented at least semiannually to assess safety and efficacy data on each arm of the study.

---

### 10.1.7.CLINICAL MONITORING

Clinical site monitoring is conducted to ensure that the rights and well-being of trial participants are protected, that the reported trial data are accurate, complete, and verifiable, and that the conduct of the trial is in compliance with the currently approved protocol/amendment(s), with International Conference on Harmonisation Good Clinical Practice (ICH GCP), and with applicable regulatory requirement(s).

- The orthopaedic research scientist will conduct monthly centralised review of data collection to ensure completeness and accuracy.

---

### 10.1.8.DATA HANDLING AND RECORD KEEPING

---

#### 10.1.8.1.DATA COLLECTION AND MANAGEMENT RESPONSIBILITIES

Data collection is the responsibility of the clinical trial staff under the supervision of the principle investigator. The investigator is responsible for ensuring the accuracy, completeness, legibility, and timeliness of the data reported.

All source documents should be completed in a neat, legible manner to ensure accurate interpretation of data.

Hardcopies of the study visit worksheets will be provided for use as source document worksheets for recording data for each participant enrolled in the study. Data recorded in the electronic database derived from source documents should be consistent with the data recorded on the source documents.

Clinical data (including adverse events (AEs), concomitant medications, and expected adverse reactions data) and clinical laboratory data will be entered into the adverse event data base. The data system includes password protection and internal quality checks, such as automatic range checks, to identify data that appear inconsistent, incomplete, or inaccurate. Clinical data will be entered directly from the source documents.

---

#### 10.1.8.2.STUDY RECORDS RETENTION

Study documents should be retained for a minimum of **30** years after completion the study intervention. These documents should be retained for a longer period, however, if required by local regulations.

---

### 10.1.9.PROTOCOL DEVIATIONS

A protocol deviation is any noncompliance with the clinical trial protocol. The noncompliance may be either on the part of the participant, the investigator, or the study site staff. As a result of deviations, corrective actions are to be developed by the site and implemented promptly.

It is the responsibility of the principle investigator to use continuous vigilance to identify and report deviations within 10 working days of identification of the protocol deviation, or within 10 working days of the scheduled protocol-required activity.

---

### 10.1.10.PUBLICATION AND DATA SHARING POLICY

This study will be conducted in accordance with the following publication and data sharing policies and regulations:

National Health and Medical Research Council (NHMRC) Public Access Policy, which ensures that the public has access to the published results of NHMRC supported research. It requires scientists to submit final peer-reviewed journal manuscripts to the digital archive PubMed Central upon acceptance for publication.

This study will comply with the NHMRC Data Sharing Policy and Policy on the and the Clinical Trials Registration and Results Information Submission rule. As such, this trial will be registered at [nhmrc.gov.au](http://nhmrc.gov.au), and results information from this trial will be submitted to [nhmrc.gov.au](http://nhmrc.gov.au). In addition, every attempt will be made to publish results in peer-reviewed journals. Data from this study may be requested from other researchers 15 years after the completion of the primary endpoint by contacting the principle investigator or a representative at the Women's and Children's Hospital.

---

### 10.1.11.CONFLICT OF INTEREST POLICY

The independence of this study from any actual or perceived influence, such as by the pharmaceutical industry, is critical. Therefore, any actual conflict of interest of persons who have a role in the design, conduct, analysis, publication, or any aspect of this trial will be disclosed and managed. Furthermore, persons who have a perceived conflict of interest will be required to have such conflicts managed in a way that is appropriate to their participation in the design and conduct of this trial. The study leadership in conjunction with the Women's and Children's Hospital Ethics Committee has established policies and procedures for all study group members to disclose all conflicts of interest and will establish a mechanism for the management of all reported dualities of interest.

---

## 10.2. ADDITIONAL CONSIDERATIONS

Not Applicable

### 10.3. ABBREVIATIONS

AE	Adverse Event
ANZCA	Australia and New Zealand College of Anaesthetists
ASA	American Society of Anaesthesiology Score - global score which assesses the physical status of patients before surgery
CRF	Case Report Form
CKD	Chronic Kidney Disease
DTC	Drug and Therapeutics Committee
FCM	Ferric Carboxymaltose
Fe	Elemental Iron
Hb	Haemoglobin concentration
ICH-GCP	International Conference on Harmonisation Good Clinical Practice
IDA	Iron Deficient Anaemia
IBW	Ideal Body Weight
IV	Intravenous
MDU	Medical Day Unit
NHMRC	National Health and Medical Research Council
NPS	National Prescriber System
PI	Principal Investigator
RDR	Rapid Detection and Response Paediatric Observation Chart
SAE	Serious Adverse Event
SRS30	Scoliosis Questionnaire Version 30
TGA	Therapeutic Goods Administration
WCH	Women's and Children's Hospital

12. APPENDIXES

APPENDIX A - INTERPRETATION OF IRON STUDIES

# Interpretation of Iron Studies

**APPENDIX D - DATA COLLECTION FORMS**

**CORRECTION OF PREOPERATIVE IRON DEFICIENCY IN CHILDREN UNDERGOING ELECTIVE SPINAL FUSION.**

**BASELINE DATA SHEET**

**6 weeks preoperative**

URN: \_\_\_\_\_  
 Date of Birth: \_\_\_/\_\_\_/\_\_\_\_  
 Gender: \_\_\_\_\_  
 Today's Date: \_\_\_/\_\_\_/\_\_\_\_  
 Date of surgery (if known): \_\_\_/\_\_\_/\_\_\_\_

Baseline Data	
Height (cm)	
Weight (kg)	
Heart Rate (bpm)	
Blood Pressure (mmHg)	
Saturations	
History of Thalassaemia, Inflammatory Bowel Disease, Arthritis, or Vasculitis?	Yes / No
Paperwork	Completed
Patient Information Sheet Provided to Patient	
Informed Consent	
SRS 30	
Bloods Requested:	
Full Blood Count	
Iron Studies	
Group and Hold	
Electrolytes	

---

**CORRECTION OF PREOPERATIVE IRON DEFICIENCY IN CHILDREN UNDERGOING ELECTIVE SPINAL FUSION.**

**REVIEW OF  
BASELINE  
RESULTS**

5 weeks  
preoperative

URN: \_\_\_\_\_  
Date of Birth: \_\_\_/\_\_\_/\_\_\_\_  
Today's Date: \_\_\_/\_\_\_/\_\_\_\_  
Date of surgery (if known): \_\_\_/\_\_\_/\_\_\_\_

Blood Results	
Haemoglobin	
MCV	
Blood Film Comment	
Ferritin	
Iron	
Transferrin	
Transferrin Saturation	
Phosphate	
Serum Calcium	
Vitamin D Level	

**Does Patient meet exclusion criteria?** (see protocol)

**Yes** - Please list: \_\_\_\_\_

**Does Patient Qualify for Iron therapy?** (Use the Interpretation of Iron Studies Flow Chart)

**No** - Inform patient/parent of results and the need for no further treatment before surgery

**Yes** - Randomise patient then inform patient/parent of results and arrange appointments as required by randomisation.

**Group Allocation:** (circle one)

**Oral Iron Therapy**

**IV Iron Therapy**

**Excluded**

---

---

**CORRECTION OF PREOPERATIVE IRON DEFICIENCY IN CHILDREN UNDERGOING ELECTIVE SPINAL FUSION.**

**INTRA-OP**

**Day of Surgery**

URN: \_\_\_\_\_

Date of Birth: \_\_\_\_/\_\_\_\_/\_\_\_\_

Date of surgery: \_\_\_\_/\_\_\_\_/\_\_\_\_

**Please send blood for Full Blood Count, Iron Studies, and Electrolytes at induction PRIOR to fluid administration**

Admission Data	
Height (cm)	
Weight (kg)	
Heart Rate (bpm)	
Blood Pressure (mmHg)	
Saturations	
ASA	
Intra operative	
Spinal Levels Fused	
Duration of Surgery	
Estimated Blood Loss	
Cell Salvage Volume	
Volume of Crystalloid	
Volume of Colloid	
Volume and type of Transfusion	

**CORRECTION OF PREOPERATIVE IRON DEFICIENCY IN CHILDREN UNDERGOING ELECTIVE SPINAL FUSION.**

**IN PATIENT DATA SHEET**

URN: \_\_\_\_\_

Date of Birth: \_\_\_/\_\_\_/\_\_\_

Date of surgery: \_\_\_/\_\_\_/\_\_\_

**0-7 days postoperative**

Date of discharge: \_\_\_/\_\_\_/\_\_\_

	Day 1	Day 2	Day 3	Day 4	Day 5	Day 6	Day 7
Haemoglobin							
Transfused (yes/no)							
Observations stable (yes/no)							
Phosphate Level							
Day of discharge							

**Please complete a Full Blood Examination on Day 1-2 and Day 5-7 and at least one test of Electrolytes including Calcium Magnesium and Phosphate "ELC" prior to discharge**

**If randomised to oral iron therapy:**

- Please collect the patient compliance survey
- Count any remaining doses. Remaining Tablets/Volume: \_\_\_\_\_

**If patient was transfused please detail the indications:**

\_\_\_\_\_

\_\_\_\_\_

\_\_\_\_\_

**If patient was not discharged prior to day 7 please detail the indications for increased duration of admission:**

\_\_\_\_\_

\_\_\_\_\_

\_\_\_\_\_

**CORRECTION OF PREOPERATIVE IRON DEFICIENCY IN CHILDREN UNDERGOING ELECTIVE SPINAL FUSION.**

**POST OPERATIVE DATA SHEET**

URN: \_\_\_\_\_  
 Date of Birth: \_\_\_/\_\_\_/\_\_\_\_  
 Date of surgery: \_\_\_/\_\_\_/\_\_\_\_

**6-12 weeks postoperative**

Study Conclusion Data		Date
Height (cm)		
Weight (kg)		
Heart Rate (bpm)		
Blood Pressure (mmHg)		
Saturations		
SRS 30 Completed		

Blood Results	2-4 weeks post-op	6-12 weeks post-op
Date of Test		
Haemoglobin		
MCV		
Blood Film Comment		
Ferritin		
Iron		
Transferrin		
Transferrin Saturation		
Phosphate		

**APPENDIX E - PATIENT COMPLIANCE QUESTIONNAIRE**

**CORRECTION OF PREOPERATIVE IRON DEFICIENCY IN CHILDREN UNDERGOING ELECTIVE SPINAL FUSION.**

**ORAL IRON QUESTIONNAIRE**

URN: \_\_\_\_\_

Date of Birth: \_\_\_/\_\_\_/\_\_\_

Date of surgery: \_\_\_/\_\_\_/\_\_\_

**Collect While Inpatient**

Iron Dosing Data	Liquid	Tablets
Date Iron Initiated		
Dose Prescribed	_____ mL/day	_____ Tabs/day
Typical Dose Taken	_____ mL/day	_____ Tabs/day

**How many days per week did your child take the oral iron supplements?**

Dosing	Everyday (7days)	Most Days (5-7days)	Some Days (3-4days)	Rarely (1-2days)	None (0days)
First Week					
Second Week					
Third Week					
Fourth Week					
Fifth Week					

**Please list any reasons why your child was unable to take the iron supplements daily:**

\_\_\_\_\_

\_\_\_\_\_

\_\_\_\_\_

**How many days per week did your child experience the following symptoms?**

Side Effects	Everyday (7days)	Most Days (5-7days)	Some Days (3-4days)	Rarely (1-2days)	None (0days)
Nausea					
Constipation					
Diarrhea					
Abdominal Pain					
Other					

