#### 6.4. STUDY INTERVENTION COMPLIANCE

Compliance with the control arm (oral iron therapy) will be assessed two ways.

1. We will ask patients/parents to return any unused iron tablets/liquid to the orthopaedic nurse consultant who will count the remaining tablets/liquid. This will be used to estimate patient medication compliance.
2. Patients/parents will be presented with a compliance questionnaire to survey their overall usage and detail any complaints or side effects. (see Appendix E)

Compliance to the treatment arm (IV ferric carboxymaltose) will be clearly documented in the patient record of attendance at the medical day unit and the patient drug chart.

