#### Prior to discharge - Day 5 (+/-2 days) Postoperative

Patients will undergo routine:

- Measure of vital signs
- Collection of blood for Full Blood Exam

- This will occur one day prior to discharge or at 7 days postoperatively (whichever is sooner)
- Documentation of any transfusion
- Patients will be asked to complete their oral iron therapy compliance questionnaire

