## 8.2. SAFETY AND OTHER ASSESSMENTS

### Intravenous Carboxymaltose

Patients presenting for their infusion of IV ferric carboxymaltose will have a baseline set of vital signs recored by the MDU nurses. They will continue to have their vitals monitored during and for 45 minutes following the infusion.

Any vitals outside the acceptable range (according to the age appropriate RDR chart) will result in the infusion being stopped and the orthopaedic resident medical officer or medical emergency team being contacted for further advise. Any evidence or report of difficulties breathing or a developing rash will result in the immediate discontinuation of the infusion and the medical emergency team will be called to review the patient.

Patients and their parents will be provided with a contact number for one of the investigators and encouraged to report any adverse events/side effects.

All adverse events will be recorded on the patient data sheet and immediately feedback to the investigators.

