#### 8.3.5. ADVERSE EVENT REPORTING

All adverse events will be recorded and collated by the investigators. The data will be collected from each participants data sheet that is completed at each of their study visits. The incidence of expected adverse events will be reported in the published data along with the occurrence and incidence of unexpected adverse events.

---

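### Only the oral arm gets a prompted side-effect grid, completed after spinal surgery with no recall period; if it feeds the published incidence, gastrointestinal rates will not be comparable between arms

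*Protocol*

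**What the plan says.** Section 8.3.4 has the investigator ask about adverse events at every study visit, in both arms, and lists what to record: description, onset, severity, relationship and resolution. The Schedule of Activities has an adverse-event review row.

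The oral arm has one more source. Section 6.4 introduces a questionnaire to "survey their overall usage and detail any complaints or side effects". Its symptom grid in Appendix E asks "How many days per week did your child experience the following symptoms" and lists nausea, constipation, diarrhoea, abdominal pain and other. The in-patient data sheet requests it under "If randomised to oral iron therapy". The form itself is marked "Collect While Inpatient". Section 8.1, in the pre-discharge assessment at Day 5 (+/-2 days), states: "Patients will be asked to complete their oral iron therapy compliance questionnaire".

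The IV arm has no counterpart. Section 6.4 says "Compliance to the treatment arm (IV ferric carboxymaltose) will be clearly documented in the patient record of attendance at the medical day unit" and on the drug chart.

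On recording, Section 8.2 says for the IV arm: "All adverse events will be recorded on the patient data sheet". Section 8.3.5 says of all adverse events: "The data will be collected from each participants data sheet that is completed at each of their study visits". It also commits to publishing the incidence of expected and unexpected events.

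**The concern.** Prompted questions usually bring out more symptoms than open ones. Here the prompt is given in one arm only, in an open-label trial, and during recovery from an operation that can itself cause most of the listed symptoms. Nausea is listed in Section 2.3.1 as an effect of both treatments but is prompted for only one.

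The primary endpoint is not affected. What is at stake is the tolerability information. Sections 2.3.3 and 4.2 set the added cost and risk of IV iron against an oral therapy described as often poorly tolerated, and readers will look to the published side-effect rates for evidence on that. An analysis plan cannot recover symptoms that were never asked about. Nor can it separate surgical symptoms from iron symptoms once both are in the same cell.

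**Working it through.** The plan states no figure on this point, so there is nothing to reproduce. The check sets the sections side by side and adds simple day and proportion arithmetic.

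**1. How side effects are found in each arm**

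| Source | Oral | IV |
|---|---|---|
| Open inquiry at each study visit (8.3.4) | yes | yes |
| Contact number for self-report (8.1, 8.2) | yes | yes |
| Staff observation at dosing (8.1, 8.2) | no | vital signs during infusion and for 45 minutes after |
| Prompted symptom grid (Appendix E) | yes | no |

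The contrast is therefore inquiry plus grid against inquiry plus observed infusion.

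**2. When the grid is completed.** Oral iron ends on Day -1 (Section 8.1). The Schedule of Activities puts the questionnaire in the in-hospital column, Days 1-5. Section 8.1 puts it at Day 5 +/- 2, that is Day 3 to Day 7, which is 3 - (-1) = 4 to 7 - (-1) = 8 days after the last dose. Either way it follows surgery. The exception is a patient who stops oral iron early, for whom Section 7.1 collects the questionnaire at that time.

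**3. What period it covers.** The dosing grid in the same form has separate rows for the first to fifth week. The symptom grid has one row per symptom, no week and no stated start or end.

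**4. Whether dates would screen out ward symptoms.** Section 8.3.4 records non-serious events until 7 days after the last iron.
- Oral: -1 + 7 = Day +6.
- IV, single dose on Day -35 to -21: -35 + 7 = -28 to -21 + 7 = -14.
- IV, second dose one week later (Section 6.1.2), Day -28 to -14: closes on Day -21 to -7.

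A ward symptom up to Day 6 is thus recordable in the oral arm, while the IV window has closed before surgery. The unequal windows are a separate matter. Aligning them would not give the IV arm a grid or give the grid a recall period.

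**5. Where else events could be recorded.** Appendix D has five sheets: baseline, review of baseline results, intra-operative, in-patient and post-operative. None has a field for an adverse event or for the items in Section 8.3.4. The nearest are a yes/no entry on stable observations, phosphate, and free text on transfusion and on stay past day 7. No sheet covers the infusion visit. The table of contents puts Appendix D at page 6 and Appendix E at page 11, which fits the five sheets shown, so a missing adverse-event page is unlikely.

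**6. Size.** The documents give neither the share of symptoms that open inquiry detects nor the frequency of these symptoms after this surgery. What can be computed is the leverage of one patient: 1/17 = 5.9 percentage points on the oral rate.

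**The case against.** The strongest reply is that the questionnaire is a compliance tool. Section 6.4 presents it as one of two compliance measures, and it sits in Appendix E rather than among the data sheets named in Section 8.3.5. No section says its answers are counted as adverse events, or that side-effect rates will be compared between arms. This stands. A reader might infer that the published rates will certainly compare two different instruments, but the documents support that only conditionally. The condition is plausible, because Section 6.4 gives the form a side-effect purpose and no other form shown could supply such rates.

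A reader might also infer that IV patients alone are left to open inquiry, or that detection favours IV iron throughout. Neither is supported: both arms get the inquiry, and observation of the infusion makes detection of acute reactions stronger in the IV arm. The likely direction of bias is limited to gastrointestinal symptoms.

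A third tempting step is to attach a size. If 30% of each arm had symptoms and open inquiry found 30% to 70% of what a checklist finds, the report would be 30% oral against 0.30 x 0.3 = 9% to 0.30 x 0.7 = 21% IV, with no true difference. Every input there is assumed. Section 2.3.1 gives treatment-related nausea of 3.1% with ferric carboxymaltose and lists no other gastrointestinal effect above 1%. At 3.1%, the same capture range would hide only 0.031 x 0.3 = 0.9 to 0.031 x 0.7 = 2.2 points. The illustration is no guide to this trial.

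It is also fair that the form's title and the weekly dosing grid before it point families towards the dosing weeks, so postoperative contamination is possible rather than shown. Safety is not an endpoint in Section 3, and Section 9.4.4 disclaims power for it; that concerns precision and does not remove a systematic difference in how symptoms are sought. Finally, Sections 7.2, 8.3.4 and 10.1.8.1 mention a case report form, an unspecified collection form and an adverse-event database, so the missing field alone is largely form housekeeping.

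**Conclusion.** The point holds in a limited form. Followed as written, the forms seek gastrointestinal symptoms harder in the oral arm than in the IV arm, and do so when surgery can produce the same symptoms. If the grid answers enter the incidence published under Section 8.3.5, those rates would not be comparable between arms and would probably be too high for oral iron. This rests on two assumptions that the documents do not settle: that the grid is used for adverse-event reporting, and that some families include the postoperative days in their answers. The size cannot be derived from the documents. The conclusion does not extend to acute infusion reactions or to the efficacy endpoints. It is an inexpensive improvement worth making, not a flaw that threatens the trial's main question.

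**What to change.** - Give both arms the same symptom checklist on Day 0, at admission and before surgery, worded to cover the time from the start of trial iron up to surgery. Include the effects that Section 2.3.1 lists for either treatment; that adds vomiting, headache, dizziness and injection-site reactions to the present grid.
- Keep the questions on doses taken for the oral arm only.
- Add an adverse-event line with the Section 8.3.4 items to the data sheets, and provide somewhere to record events at the infusion visit.
- State in Section 8.3.5 whether checklist answers count as adverse events, and report prompted and spontaneously reported events separately.

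The cost is revised Appendix D and E forms, matching edits to Section 8.1 and the Schedule of Activities, and slight extra form time for IV patients. No visit is added, since all patients already attend on Day 0, and by then oral iron has ended. Recall would reach back 3-5 weeks to the start of treatment, but equally in both arms.
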